14.2.3.3. Colorimetry

Table 28. Colorimetry CEI: % change from baseline (ITT)

	IVM + Doxycycline	IVM + Vehicle	p-value (1)
Week4			XXX
N			
Mean ±SD			
Median			
Min,Max			
Week 12			XXX

⁽¹⁾ p-value of CMH test based on ridit scores stratified by analysis-center.

14.2.4. Patient reported outcomes

14.2.4.1. Dermatology Life Quality Index

Table 29. DLQI at baseline - Descriptive (ITT)

	IVM + Doxycycline	IVM + Vehicle
1. DLQI itch, sore, painful, stinging?		
N		
0: Not at all		
1: A little		
2: A lot		
3: Very much		
10. DLQI problem caused by treatment?		
N		
0: Not at all		
0: Not relevant		
1: A little		
2: A lot		
3: Very much		

Table 30. DLQI at last visit - Descriptive (ITT)

Table 31. DLQI: Total score at each visit and percent change from baseline (ITT)

	IVM + Doxycycline	IVM + Vehicle	p-value
Baseline (Total score)			
N			NA
0-1: No effect at all on patient's life			
2-5: Small effect on patient's life			
6-10: Moderate effect on patient's life			
Mean±SD			
Median			
(Min,Max)			
Last visit (Total score)			XXX
•••			
Last visit (% change from Baseline)			
N			XXX
Mean±SD			
Median			
(Min,Max)			

⁽¹⁾ p-value by CMH test based on ridit scores stratified by analysis-center.

14.2.4.2. EQ-5D-5L questionnaire

Table 32. EQ-5D-5L questionnaire at baseline - Descriptive (ITT)

	IVM + Doxycycline	IVM + Vehicle
Mobility		
N		
I have no problems walking		
I have slight problems walking		
I have moderate problems walking		
I have severe problems walking		
I have unable to walk		
Self-Care		
Usual Activities		
Pain/Discomfort		
Anxiety/Depression		
Health State Today		
N		
Mean ±SD		
Median		
Min,Max		

Table 33. EQ-5D-5L questionnaire at last visit (ITT)

	IVM + Doxycycline	IVM + Vehicle	p-value (1)
Mobility			
N			XXX
I have no problems in walking about			
I have slight problems in walking about			
I have moderate problems in walking about			
I have severe problems in walking about			
I have unable to walk about			
Self-Care			
			XXX
Usual Activities			
			XXX
Pain/Discomfort			
			XXX
Anxiety/Depression			
			XXX
Health State Today			
N			XXX
Mean ±SD			
Median			
Min,Max			

⁽¹⁾ p-value by CMH test based on ridit scores stratified by analysis-center.

14.2.4.3. Work Productivity and Activity Impairment Questionnaire: General Health (WPAI:GH)

Table 34. WPAI :GH questionnaire at baseline - Descriptive (ITT)

	IVM + Doxycycline	IVM + Vehicle
Currently employed		
N		
No		
Yes		
Missed hours from work because of rosacea?		
N		
Mean ±SD		
Median		
Min,Max		
Missed hours from work because of other reason?		
Number of Working hours		
How much rosacea affect productivity at work?		
How much rosacea affect daily activity?		
N		
Mean ±SD		
Median		
Min,Max		

Table 35. WPAI :GH questionnaire at last visit (ITT)

	IVM + Doxycycline	IVM + Vehicle	p-value (1)
Currently employed			
N			XXX
No			
Yes			
Missed hours from work because of rosacea?			XXX
N			
Mean ±SD			
Median			
Min,Max			
Missed hours from work because of other reason?			XXX
Number of Working hours			XXX
How much rosacea affect productivity at work?			XXX
How much rosacea affect daily activity?			XXX
N			
Mean ±SD			
Median			
Min,Max			

⁽¹⁾ p-value by CMH test based on ridit scores stratified by analysis-center.

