7.3.2 EQ-5D-5L questionnaire

Subjects will answer the quality of life questionnaire EQ-5D-5L at Baseline visit and at last visit. EQ-5D-5L is a 5-level, 5-dimensional format standardized instrument for use as a measure of health outcome. Applicable to a wide range of health conditions and treatments, it provides a simple descriptive profile and a single index value for health status. EQ-5D was originally

Protocol N° RD.03.SPR.113322

version Final dated 10-FEB-2017

Page 62 of 106 CONFIDENTIAL

designed to complement other instruments but is now increasingly used as a 'stand-alone' measure. EQ-5D-5L is designed for self-completion by respondents. It is cognitively simple; taking only a few minutes to complete (see section 13.2). The investigator or delegate will then check all questions of the questionnaire for completeness prior to the subject leaving the study visit.

7.3.3 Work Productivity and Activity Impairment Questionnaire: General Health Problem (WPAI:GH) modified for Rosacea.

Subjects will answer the quality of life questionnaire WPAI: GH at Baseline visit and at last visit. The WPAI: GH questionnaire consists of six questions (see section 13.3). It is an instrument to measure impairments in both paid work and unpaid work. It measures absenteeism, presenteeism as well as the impairments in unpaid activity because of health problem during the past seven days. It has been validated to quantify work impairments for numerous diseases including dermatological diseases such as psoriasis^{1.16}. In addition, the WPAI: GH questionnaire has been used to compare work impairments between treatment groups in clinical studies or between subjects with different disease severity levels. As per WPAI questionnaire adaptation guidelines, the questionnaire has been adapted for rosacea by replacing the term 'your health problems' by 'your rosacea'.

The investigator or delegate will then check all questions of the questionnaire for completeness prior to the subject leaving the study visit.

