7.5 APPROPRIATENESS OF MEASUREMENTS

The clinical efficacy assessments will be based on inflammatory lesion counts, evaluation of facial erythema, stinging/burning sensation and flushing. The methods are established in the evaluation of rosacea products and used in previous studies with the study products.

Safety is documented by recording adverse events on an ongoing basis as a well-established process in clinical trials. In case of reporting of a worsening of rosacea, specific complementary data will be collected.

Impact of study treatments on subjects' quality of life will be measured by using specific questionnaires. DLQI and EQ-5D-5L are two validated questionnaires for evaluating quality-of-life: While EQ-5D-3L is more general and not disease-specific, the DLQI focuses on the impact of dermatological diseases on the quality-of-life.

The WPAI:GH questionnaire is a validated instrument to quantify work impairments for numerous diseases including dermatological conditions.

To collect specifically the patient satisfaction outcome, a subject satisfaction questionnaire will be used at the end of the study to collect the subjects' feedback on the treatment regimen, the level of satisfaction and future usage.

Protocol N° RD.03.SPR.113322

version Final dated 10-FEB-2017

Page 64 of 106 CONFIDENTIAL

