9.1.1.5 Patient Reported Outcomes (PRO)

- DLQI questionnaire at Baseline and the last visit
- EQ-5D-5L questionnaire at Baseline and last visit
- WPAI:GH questionnaire at Baseline and last visit
- Subject Satisfaction Questionnaire at last visit

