	If NO, check "NO" and skip to question 6.
The	next questions are about the past seven days , not including today.
2.	During the past seven days, how many hours did you miss from work because of your rosacea ? Include hours you missed on sick days, times you went in late, left early, etc., because of your rosacea. Do not include time you missed to participate in this study. HOURS
3.	During the past seven days, how many hours did you miss from work because of any other reason, such as vacation, holidays, time off to participate in this study? HOURS
4.	During the past seven days, how many hours did you actually work? HOURS (If "0", skip to question 6.)

Protocol N° RD.03.SPR.113322

version Final dated 10-FEB-2017

Page 93 of 106 CONFIDENTIAL

5. During the past seven days, how much did your rosacea affect your productivity while you were working?

Think about days you were limited in the amount or kind of work you could do, days you accomplished less than you would like, or days you could not do your work as carefully as usual. If rosacea affected your work only a little, choose a low number. Choose a high number if rosacea affected your work a great deal.

Consider only how much rosacea affected productivity while you were working.

Rosacea had no												Rosacea
effect on my work	0	1	2	3	4	5	6	7	8	9	10	 completely prevented me from working

CIRCLE A NUMBER

6. During the past seven days, how much did your rosacea affect your ability to do your regular daily activities, other than work at a job?

By regular activities, we mean the usual activities you do, such as work around the house, shopping, childcare, exercising, studying, etc. Think about times you were limited in the amount or kind of activities you could do and times you accomplished less than you would like. If rosacea affected your activities only a little, choose a low number. Choose a high number if rosacea affected your activities a great deal.

Consider only how much rosacea affected your ability to do your regular daily activities, other than work at a job.

Rosacea had no	Rosacea

Protocol N° RD.03.SPR.113322

version Final dated 10-FEB-2017

Page 94 of 106 CONFIDENTIAL

effect on my daily 0 1 2 3 4 5 6 7 8 9 10 completely activities from doing my daily activities

CIRCLE A NUMBER

WPAI:GH V2.0 (US English) modified for Rosacea

Very satisfied

Satisfied

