4.2 PATIENT-REPORTED OUTCOMES VARIABLES

> Dermatology Life Quality Index (DLQI) at week12/early termination: % of subject across Total score at baseline and last visit; and the % change from baseline.

Grade	Description
0-1	No effect at all on patient's life
2-5	Small effect on patient's life
6-10	Moderate effect on patient's life
11-20	Very large effect on patient's life
21-30	Extremely large effect on patient's life

- ➤ EQ-5D questionnaire at week12/early termination: % of subjects across score of questions at baseline and last visit.
- > Work Productivity and Activity Impairment Questionnaire at week 12/early termination: General Health (WPAI: GH) modified for Rosacea. % of subjects across score of questions at baseline and last visit.
- > Subject's satisfaction questionnaire at week12/early termination: % of subjects across score of questions at last visit.

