6.4 PATIENT-REPORTED OUTCOMES ANALYSES

DLQI, EQ-5D-5L, WPAI-GH and subject satisfaction questionnaires will be statistically analyzed similarly as primary analyses on ITT population at each post-baseline evaluation time.

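### The WPAI analysis tests six raw items, three of them not rosacea impairments; absenteeism is not related to working time and baseline is not used

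*SAP*

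**What the plan says.** Protocol 7.3.3 describes the instrument: "It measures absenteeism, presenteeism as well as the impairments in unpaid activity because of health problem during the past seven days". Protocol 7.5 gives its purpose: "The WPAI:GH questionnaire is a validated instrument to quantify work impairments for numerous diseases including dermatological conditions". Protocol 9.1.1.5 lists the variable only as "WPAI:GH questionnaire at Baseline and last visit", with no score defined.

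SAP 4.2 defines the WPAI variable as the percentage "of subjects across score of questions at baseline and last visit". SAP 6.4 sets the test: "DLQI, EQ-5D-5L, WPAI-GH and subject satisfaction questionnaires will be statistically analyzed similarly as primary analyses on ITT population at each post-baseline evaluation time". SAP 6 makes all tests two-sided at 0.05.

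SAP Table 35 (section 14.2.4.3) has six rows for the last visit: employment status, hours missed because of rosacea, "Missed hours from work because of other reason", hours worked, effect on productivity at work, and effect on daily activity. Each row has a p-value, footnoted "p-value by CMH test based on ridit scores stratified by analysis-center". Table 34 shows the same items at baseline, descriptively. No change from baseline is planned for the WPAI. For the DLQI, in contrast, Table 31 tests a total score and a percent change from baseline.

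The questionnaire (Protocol Attachment 3) also collects working time: "During the past seven days, how many hours did you actually work".

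**The concern.** The protocol names three constructs, but the SAP tests questions. Three consequences follow.

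- **Absenteeism has no denominator.** Hours missed because of rosacea are ranked as they stand, whether the subject had a short or a full working week.
- **Some tests do not address the treatment question.** Employment status, hours missed for other reasons and hours worked are not impairments attributed to rosacea. Attachment 3 gives holidays and time off for the study itself as examples of other reasons. A p-value below 0.05 on such a row could be reported as a treatment finding without being one.
- **Baseline is collected but not used.** Every WPAI comparison is of last-visit values alone.

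At stake is how clearly the work-impairment results can be read. The WPAI is listed among the patient-reported outcomes, apart from the primary and secondary efficacy variables.

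**Working it through.** **Plan's own figure.** Neither document states a sample size, effect size or error rate for the WPAI, so there is nothing to reproduce. The only sample-size figure, 114 evaluable and 135 enrolled per group, is for lesion counts and has no bearing here.

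**1. Items against constructs** (Attachment 3, Protocol 7.3.3, Table 35)

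| Question | Content | Construct | Who answers |
|---|---|---|---|
| 1 | Employed | none | all |
| 2 | Hours missed, rosacea | absenteeism, raw hours | employed |
| 3 | Hours missed, other reason | none | employed |
| 4 | Hours worked | none by itself; usable as part of a denominator | employed |
| 5 | Productivity at work, 0–10 | presenteeism | employed and worked that week |
| 6 | Daily activities, 0–10 | activity impairment | all |

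The last column follows from the skip instructions: a subject who is not employed goes from question 1 to question 6, and a subject with zero hours worked goes from question 4 to question 6. Table 35 is labelled ITT and does not state these restrictions.

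**2. Does using raw questions 5 and 6 lose anything?** The ridit CMH test depends only on ranks within center. Multiplying a 0–10 item by 10 to give a percentage leaves the ranks unchanged. In a simulated data set of 270 subjects in 27 strata, the statistic was 0.1498 in both forms. Nothing is lost by testing the raw items.

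**3. Does using raw hours for absenteeism lose anything?** Assumed ratio: A = Q2 / (Q2 + Q4).

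- Missed 4, worked 4: A = 4/(4+4) = 50%.
- Missed 4, worked 36: A = 4/(4+36) = 10%.

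Raw hours tie these two subjects and the ratio separates them, so the ranks and the test statistic can change. In one simulated draw (Poisson missed hours with mean 0.8; 8, 20 or 40 hours worked) the statistic was 2.34 on raw hours and 2.73 on the ratio. These values are illustrative. They show that the statistic moves, not which measure is more sensitive.

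The ratio is 0/0 for an employed subject who neither worked nor missed rosacea hours, for example one on holiday, so a rule is needed.

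**4. False positives with no treatment effect, unadjusted 0.05**

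- Three non-impairment rows: 3 × 0.05 = 0.15 expected. This needs no independence assumption. Counting only employment and other-reason hours gives 2 × 0.05 = 0.10.
- At least one among six tests, if independent: 1 − 0.95^6 = 0.265. Whatever the dependence, the upper bound is 6 × 0.05 = 0.30.
- At least one among three tests, if independent: 1 − 0.95^3 = 0.143, upper bound 3 × 0.05 = 0.15.

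Cutting to three tests lowers the risk but does not control it at 0.05.

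**The case against.** The strongest reply is that the SAP is internally consistent. SAP 4.2 defines the variable by question and Table 35 follows that definition. Neither document defines an absenteeism ratio, so the SAP breaks no stated scoring rule. This stands: the point is an improvement, not a contradiction between the documents.

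A reader might infer that item-level testing replaces the three constructs and leaves the work-impairment question unanswered. The documents do not support that. Table 35 tests questions 5 and 6, which carry presenteeism and activity impairment, and a rank test is indifferent to rescaling them. Hours missed because of rosacea is also tested. The question is answered in part.

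Nor do the documents show that raw hours misstate the result. Raw hours are an interpretable quantity, though a different one. A working subject with no rosacea hours missed scores zero either way, so the two measures can order subjects differently only among those who missed some time. The documents give no distribution of missed or worked hours, so the practical size of the difference is unknown.

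It can also be said that hours worked is a work outcome. That is fair, but question 4 does not attribute those hours to rosacea. Its more useful role is in the denominator.

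Finally, the planned CMH test takes no covariate. Asking only for baseline adjustment would therefore be incomplete, and a method has to be named.

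**Conclusion.** The point holds as a cheap improvement to a non-primary outcome. Absenteeism is tested without reference to working time. Three of six p-values concern no impairment attributed to rosacea, at 0.15 expected false positives (0.10 if hours worked is accepted as an outcome in its own right). No WPAI comparison uses baseline.

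The absenteeism ratio is an assumption built from questions 2 and 4; no scoring manual is in the documents. The family-wise figures of 0.265 and 0.143 assume independent tests. The 50% against 10% contrast is a constructed example. The primary conclusion is unaffected.

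**What to change.** Amend SAP 4.2, SAP 6.4 and Table 35:

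1. Define absenteeism as Q2 / (Q2 + Q4) in employed subjects. State that it is an assumption built from the collected items, and set it to missing when Q2 + Q4 = 0.
2. Test only absenteeism, question 5 (subjects who worked) and question 6 (all subjects). Label these tests exploratory and print each denominator.
3. Account for baseline with a named method: either a center-stratified rank ANCOVA, or the planned ridit CMH test on change from baseline in subjects with both values.
4. Show employment, other-reason hours and hours worked descriptively, without p-values.

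The cost is one derived variable, a few sentences of SAP text, three p-values removed, and programming for the baseline method; the CMH test on change is the lighter option. No new data are needed.

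The downside is smaller and selected analysis sets. Absenteeism and presenteeism apply only to subjects who are employed or working at the visit, which is determined after randomisation. The baseline-adjusted comparisons include only subjects with values at both visits. The SAP should state both limits.

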14.2.4.4. Subject's satisfaction questionnaire

Table 36. Subject's satisfaction questionnaire – Part A at last visit (ITT)

Questions about study drugs	IVM +	IVM +	p-value (1)
	Doxycycline	Vehicle	
1. How satisfied are you with the amount of time the study			
regimen took to work?			
N			XXX
Very satisfied			
Satisfied			
Somewhat satisfied			
Not satisfied			
12. How did you find the study regimen compared to your last			
treatment?			
N			XXX
A lot better			
Better			
Similar			
Worse			
Never treated with a previous treatment			

⁽¹⁾ p-value by CMH test based on ridit scores stratified by analysis-center.

Table 37. Subject's satisfaction questionnaire – Part B at last visit (ITT)

Questions about skin care products Cleanser and Moisturizer	IVM +	IVM +	p-value (1)
	Doxycycline	Vehicle	
1. Both skin care products easy to incorporate into a daily			
routine			
N			XXX
Strongly agree			
Agree			
Neither agree or disagree			
Disagree			
Strongly disagree			
10. Both skin care products are pleasant to use?			
N			XXX
Strongly agree			
Agree			
Neither agree or disagree			
Disagree			
Strongly disagree			

⁽¹⁾ p-value by CMH test based on ridit scores stratified by analysis-center.

Table 38. Subject's satisfaction questionnaire – Part C at last visit (ITT)

Questions about the cosmetic product cleanser	IVM +	IVM +	p-value (1)
	Doxycycline	Vehicle	
1. The Cleanser left my skin with a clean healthy feeling			
N			XXX
Strongly agree			
Agree			
Neither agree or disagree			
Disagree			
Strongly disagree			
4. The Cleanser did not make my skin feel tight or dry			
N			XXX
Strongly agree			
Agree			
Neither agree or disagree			
Disagree			
Strongly disagree			

⁽¹⁾ p-value by CMH test based on ridit scores stratified by analysis-center.

Table 39. Subject's satisfaction questionnaire – Part D at last visit (ITT)

Questions about the cosmetic product Moisturizer	IVM +	IVM +	p-value (1)
	Doxycycline	Vehicle	
1. The Moisturizer made my skin feel soft and smooth			
N			XXX
Strongly agree			
Agree			
Neither agree or disagree			
Disagree			
Strongly disagree			
4. The Moisturizer provided a conforting sensation on the	,		
skin			
N			XXX
Strongly agree			
Agree			
Neither agree or disagree			
Disagree			
Strongly disagree			

⁽¹⁾ p-value by CMH test based on ridit scores stratified by analysis-center.

14.3 Safety analyses

14.3.1. Extent of Exposure

Table 40. Quantity of topical treatment in gram (1) used during the study (APT)

	IVM + Doxycycline	IVM + Vehicle
N		
Mean±SD		
Median		
Min,Max		

⁽¹⁾ Assumes non-returned products were used in the same way as returned products.

Table 41. Extent of exposure (days) (APT)

	IVM + Doxycycline	IVM + Vehicle
Oral treatment		
N		
Mean±SD		
Median		
Min,Max		
Topical treatment		
N		
Mean±SD		
Median		
Min,Max		

Treatment duration will be calculated as the number of days between the date of first use and the date of the last use of each study treatment (oral and topical). In case of missing data of last use, the last visit will be taken into account.

Table 42. Compliance for investigational products (APT)

	IVM + Doxycycline	IVM + Vehicle
Compliance for oral treatment		
N		
<25% of compliance		
[25%;50%[of compliance		
[50%;75%[of compliance		
>=75% of compliance		
Mean±SD		
Median		
Min,Max		
Compliance for topical treatment		
N		
<25% of compliance		
[25%;50%[of compliance		
[50%;75%[of compliance		
>=75% of compliance		
Mean±SD		
Median		
Min,Max		
Overall compliance of investigational product		
N		
<25% of compliance		
[25%;50%[of compliance		
[50%;75%[of compliance		
>=75% of compliance		
Mean±SD		
Median		
Min,Max		

Compliance= ((Date of last visit - Date of baseline) - total number of corresponding missing applications)*100/ (Date of last visit - Date of baseline).

Overall compliance is the mean of each compliance.

Table 43. Compliance for the Moisturizer (APT)

	IVM + Doxycycline	IVM + Vehicle
N		
<25% of compliance		
[25%;50%[of compliance		
[50%;75%[of compliance		
>=75% of compliance		
Mean±SD		
Median		
Min,Max		

Moisturizer compliance = total number of days where the moisturizer was used *100/ (Date of last visit – Date of baseline)

14.3.2. Adverse events

Table 44. Overview of adverse events by group (APT)

	IVN	IVM + Doxycycline (N=xxx)		M + Vehicle
				(N=xxx)
	Event	Subject* n(%)	Event	Subject* n(%)
All AEs				
All dermatologic AEs				
All worsening of rosacea AEs				
All severe AEs				
All serious AEs				
Deaths				
All AEs leading to discontinuation				
Related AEs				
Related dermatologic AEs				
Related worsening of rosacea AEs				
Related severe AEs				
Related serious AEs				
Related AEs leading to discontinuation				

^{*} Subjects with at least one event. Numbers in columns cannot be added because a given subject may have reported more than one AE.

Table 45. Frequency of all adverse events by preferred term (APT)

e.g.	IVM + Doxycycline		IVM + Doxycycline		IVM + Doxycycline		IVM +	Vehicle
	(N=xxx)		(N=	xxx)				
Abdominal pain nos	Event Subject* n(%)		Event	Subject* n(%)				
Diarrhoea nos								
Peptic ulcer								

^{*} Subjects with at least one event.

Numbers in columns cannot be added because a given subject may have reported more than one AE.

Table 46. Frequency of all adverse events (except SAE) by preferred term (APT)

Table 47. Frequency of related adverse events by preferred term (APT)

Table 48: Frequency of all adverse events by SOC and preferred term (APT)

e.g.	IVM + Doxycycline		IVM + Vehicle	
	(N=xxx)		(N=	exxx)
ANY ADVERSE EVENT	Event Subject* n(%)		Event	Subject* n(%)
GASTROINTESTINAL DISORDERS				
Abdominal pain nos				
Diarrhoea nos				
Peptic ulcer				
Vomiting nos				
IMMUNE SYSTEM DISORDERS				
Allergic sinusitis				
Conjunctivitis allergic				

^{*}Subjects with at least one event. Numbers in columns cannot be added because a given subject may have reported more than one AE.

A subject was counted once per SOC and once per preferred term even if more than one occurrence of an event was reported within a SOC or preferred term.

Table 49. Frequency of related adverse by SOC and preferred term (APT)

Table 50. Subject incidence by severity of all adverse events by SOC and preferred term (APT)

e.g.	IVM + Doxycycline			IVM + Vehicle		
		(N=xxx)			(N=xxx)	
	Mild	Moderate	Severe	Mild	Moderate	Severe
	n(%)	n(%)	n(%)	n(%)	n(%)	n(%)
ANY ADVERSE EVENT						
GASTROINTESTINAL DISORDERS						
Abdominal pain nos						
Diarrhoea nos						
Peptic ulcer						
Vomiting nos						
IMMUNE SYSTEM DISORDERS						
Allergic sinusitis						
Conjunctivitis allergic						

^{*}Subjects with at least one event.

Numbers in columns cannot be added because a given subject may have reported more than one AE.

A subject was counted once per SOC (highest intensity whatever the AE within the SOC) and once per preferred term (highest intensity if more than one occurrence of an event is reported)

Table 51. Subject incidence by severity of related adverse events by SOC and preferred term (APT)

Table 52. Incidence of subject with serious adverse events by SOC and preferred term (APT)

e.g.	IVM + Doxycycline		ycycline IVM + Vehic			
	(N=xxx)		(N=xxx)		(N=	xxx)
	Event Subject* n(%)		Event	Subject* n(%)		
ANY SERIOUS ADVERSE EVENT						
GASTROINTESTINAL DISORDERS						
Abdominal pain nos						

^{*}Subjects with at least one event. Numbers in columns cannot be added because a given subject may have reported more than one AE.

A subject was counted once per SOC and once per preferred term even if more than one occurrence of an event was reported within a SOC or preferred term.

(A listing can be provided with the information of the AE form if too few SAE) Table 52. Listing of subjects with serious adverse events (APT)

(Include: subject number, treatment group, SOC, preferred term, date of onset, severity, subject discontinued, outcome, date of resolution and relationship

Table 53. Incidence of subject with adverse events leading to discontinuation of treatment by SOC and preferred term (APT)

e.g.	IVM + Doxycycline		IVM +	Vehicle
	(N=xxx)		(N=	xxx)
	Event Subject* n(%)		Event	Subject* n(%)
ANY SERIOUS ADVERSE EVENT				
GASTROINTESTINAL DISORDERS				
Abdominal pain nos				

^{*}Subjects with at least one event. Numbers in columns cannot be added because a given subject may have reported more than one AE.

(A listing can be provided with the information of the AE form if too few subjects with adverse events leading to discontinuation of treatment)

Table 53. Listing of subjects with adverse events leading to discontinuation of treatment (APT)

(Include : subject number, treatment group, SOC, preferred term, date of onset, severity, SAE, outcome, date of resolution and relationship)

Table 54. List of worsening of rosacea AEs (APT)

A subject was counted once per SOC and once per preferred term even if more than one occurrence of an event was reported within a SOC or preferred term.
